The primary risks occur during administration of lemborexant with buprenorphine-naloxone. This will take place on the clinical research unit, under supervision of providers and trained nursing staff who will immediately respond to any adverse event. Participants will spend the night on the CRU prior to lemborexant administration to ensure that they do not take any additional drugs or medications that could interact with lemborexant.

The identification of effective treatments for opioid use disorder would be a great benefit to society.

If any Psychiatric or non-Psychiatric medical illness (other than substance abuse) is discovered during the study, subjects will be referred for additional treatment in the community.

STUDY DESIGN

Overview

We propose a series of experiments to study the safety and target engagement of lemborexant when combined with buprenorphine-naloxone for opioid use disorder.

Study Design: Pharmacokinetic safety and pharmacodynamic efficacy signal trial of combined lemborexant and buprenorphine-naloxone (see Figure 1 below).

STUDY OVERVIEW/SCHEMA

[figure not shown]

Figure 1. Overall Study Design

Participants will include 18 individuals (goal of 9 male and 9 female) with opioid use disorder in medication assisted treatment who are a buprenorphine-naloxone sublingual film daily dose ranging from 8mg/2mg to 24mg/6mg or buprenorphine sublingual tablet dose ranging from 5.7mg/1.4mg to 17.1/4.3 once daily at the VCU MOTIVATE or other outpatient treatment setting who complete at least one drug-drug interaction treatment session with primary endpoint data (at least 12 lemborexant treated participants and 6 placebo treated subjects).

After a complete screening including the phenotyping assessment battery (PhAB) described in detail below,

participants will be randomized to either lemborexant (12 participants) or placebo (6 participants) and will undergo safety and PK testing on the CRSU at VCU, as described in Tables 1 and 2 below. We will characterize the pharmacokinetic (PK) and pharmacodynamic (PD) profiles of the combined administration of lemborexant with buprenorphine-naloxone including the time to onset, duration of action, magnitude of effects, and the pharmacokinetic disposition of buprenorphine and its major metabolite in plasma.

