Study Hypotheses: 1. *Adjunctive lemborexant (compared to placebo) will not alter the PK of buprenorphine-naloxone significantly, nor will it alter the pharmacodynamic properties related to safety (e.g., ECG, pulse oximetry changes, capnography, significant increases in sedation and agitation).* **Secondary hypotheses:** 2. *Adjunctive lemborexant will reduce subjective opioid craving, anxiety, opioid withdrawal, and impulsivity).* **Exploratory hypotheses:** 3. *Adjunctive lemborexant will not affect central mu opioid receptors as measured by pupillometry, but will increase subjective sleep ratings and behavioral effects of lemborexant will be related to behavioral profile measures from the NIDA phenotyping battery.*

Brief description of the protocol: The overall goal of this project is to develop initial human data for lemborexant combined with buprenorphine-naloxone on safety (e.g., interactive effects on cardiovascular and respiratory function, and agitation and sedation) and efficacy (subjective craving and anxiety, opioid withdrawal and impulsivity) in opioid use disorder participants. The sample will be recruited from VCU MOTIVATE clinic and other treatment programs and consist of participants with opioid use disorder of at least moderate severity that have been stabilized on buprenorphine-naloxone sublingual film daily dose ranging from 8mg/2mg to 24mg/6mg or buprenorphine sublingual tablet dose ranging from 5.7mg/1.4mg to 17.1/4.3 once daily.

PRIMARY Endpoints:

1. Safety: Heart rate (HR), blood pressure (BP), respiration (pulse oximetry, end tidal CO₂ (EtCO₂), respiratory rate), agitation and sedation (Richmond Agitation Sedation Scale).
2. Buprenorphine PK: Plasma concentration-time profiles of buprenorphine and its metabolite norbuprenorphine
3. Lemborexant PK: Plasma concentration-time profiles of lemborexant and its major metabolite M10.

SECONDARY Endpoints:

1. Subjective effects on opioid craving, anxiety and lemborexant drug liking as measured by a visual analog scale (VAS), and Brief Substance craving scale (BSCS), and opioid withdrawal based on the Subjective Opioid Withdrawal Scale (SOWS).
2. Objective opioid withdrawal based on the Clinical Opioid Withdrawal Scale (COWS).
3. Impulsivity as measured by a delayed discounting task (DDT).

EXPLORATORY Endpoints:

1. Change in pupil size as an indicator of central nervous system mu-opioid pharmacological effects (Rollins, Feiner et al. 2014, measured by pupillometry.).

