If subjects meet inclusion criteria, they will be admitted as research participants to the clinical research unit (CRU) for a total of up to 4 overnight stays across the two inpatient admission visits to maintain complete monitoring for adverse events. While in the hospital, subjects will undergo procedures as described below. Subjects will not be allowed to smoke cigarettes, as smoking is not allowed in the hospital or anywhere on the VCU campus. Subjects who are identified as current smokers will have the option to use a nicotine patch dosed based on the amount of daily cigarettes smoked. Subjects will not be allowed to leave the CRU nor receive visitors if they wish to remain in the study. Subjects who are unable to comply with these restrictions will be dropped from the study. Eligible subjects will be randomized to Group A –placebo only or Group B – lemborexant. Six subjects will be assigned to Group A (placebo) and 12 subjects will be assigned to Group B (active lemborexant).

Study Drug Dosage: 5 mg of lemborexant, and 10 mg of lemborexant, all subjects will receive a dose equivalent to their current prescribed dose of buprenorphine-naloxone sublingually as a film or tablet.

STUDY OUTCOME MEAURES

Primary outcome measures:

1. Safety: Heart rate (HR), blood pressure (BP), respiratory rate, agitation and sedation (Richmond Agitation-Sedation Scale), capnography (EtCO₂), and pulse oximetry during placebo administration will be compared to those same measures after lemborexant. Changes in safety measures induced by buprenorphine-naloxone dose along with lemborexant will be compared to those without lemborexant. Adverse event data will be compiled for lemborexant and placebo cohorts and presented as summary statistics.
2. Buprenorphine PK: Plasma concentration-time profiles of buprenorphine and its metabolite norbuprenorphine and after doses during the lemborexant placebo/administration (Day 0,1, 2) will be analyzed to obtain pharmacokinetic parameter estimates of buprenorphine (C_{max}, T_{max}, AUC, apparent t_{1/2}, CL/F for parent buprenorphine and metabolic (AUC) ratios for metabolites) by individual. In addition lemborexant and its main metabolite M10 will be determined after each dose of buprenorphine and compared with published lemborexant PK parameters.

Secondary Outcome Measures:

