1. Subjective effects on opioid craving and anxiety as measured by a visual analog scale, and brief substance craving scale, and opioid withdrawal based on the Subjective Opioid Withdrawal Scale.
2. Objective opioid withdrawal based on the Clinical Opioid Withdrawal Scale.
3. Impulsivity as measured by delayed discounting. All measures will be compared between subjects receiving lemborexant versus those on placebo to determine the extent to which this measure is modified by the administration of lemborexant with buprenorphine vs. placebo with buprenorphine.

Exploratory Outcome Measures:

1. Pupillometry is used to measure change in pupil size as an indicator of lemborexant changes in buprenorphine central nervous system mu-opioid pharmacological effects (Rollins, Feiner et al. 2014). Single pupil measurements at scheduled times will be performed using a pupillometer per manufacturer's specification. The light in the measurement room will be maintained at 3.6 to 4.3 lux, using a Lutron light meter. Participants will be allowed to adjust to the room lighting for at least 3 minutes prior to any measurement. Pupillometry will be measured using the right eye for all participants, unless otherwise determined by the Investigator. The same eye will be used for all measurements in the study.
2. Sleep quality as measured by sleep diary and Pittsburgh Sleep Quality Index.
3. Relationship between baseline behavioral profiles as determined by the NIDA Phenotyping Battery and subjective response to lemborexant.

STUDY DRUG AND DOSAGE

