On PK/Safety Testing week 1 Study Day 2 lemborexant (or matching placebo) is given as 5 mg at 7:00 AM after an overnight stay on the CRU. On PK/Safety Testing Week 2 Study Day lemborexant (or matching placebo) is given as 10 mg at 7:00 AM. Subjects will be continuously monitored on the CRU for 8 hours after the lemborexant dose, which is past the C_{max} lemborexant concentration, which will occur between 8:00 AM and 10:00 AM. Blood samples for determination of buprenorphine concentration and its major metabolite norbuprenorphine and lemborexant and its major metabolite M10 will be collected pre-dose and specified timepoints during the hospital stay (Table 3). Plasma levels will be utilized to determine AUC (area under the concentration–time curve from Time 0 post-dose to infinity) and $T_{1/2}$ (apparent terminal half-life) using noncompartmental analysis, and C_{max} (maximum concentration), C_{24} (concentration at 24 hours post-dose), and T_{max} (time to C_{max}). Plasma buprenorphine and norbuprenorphine and lemborexant and M10 levels will be determined in the VCU Department of Pharmacology and Toxicology drug analysis laboratory.

Dispensing: Study drug will be dispensed by the research pharmacist and administered by the research nurse on the CRU.

Supply of Study Drug at the Site: Study drug will be provided to the CRU after an order from the study physician or nurse practitioner. Storage: At the testing facility, all lemborexant, buprenorphine, and placebo must be kept in a secure, locked storage place with access limited to authorized study personnel only.

Study Drug Accountability: All study medication will be administered on the CRU. The study staff will record an accurate accounting of each medication administered.

STUDY PROCEDURES AND GUIDELINES

A Schedule of Events representing the required testing procedures to be performed for the duration of the study is diagrammed in Tables 1-2. Prior to conducting any study-related activities, written informed consent and the Health Insurance Portability and Accountability Act (HIPAA) authorization must be signed and dated by the subject. In order to better accommodate participant schedules, PK/Safety Testing Weeks 1 and 2 may be separated by up to approximately 14 days.

Clinical Assessments:**Concomitant Medications**

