All concomitant medication and concurrent therapies will be documented during screening, CRU study days, and Follow-Up days. Dose, route, unit frequency of administration, and indication for administration and dates of medication will be captured.

Clinical Opiate Withdrawal Scale (COWS) and Subjective Opiate Withdrawal Scale (SOWS)

These scales will be administered each study day during screening, admission to the CRU, and CARI or Motivate clinic study days to determine the presence of symptoms indicative of opiate withdrawal.

Demographics

Demographic information (date of birth, gender, race) will be recorded at screening.

Medical History

Relevant medical history, including history of current disease, other pertinent history, and information regarding underlying diseases will be recorded at screening.

Physical Examination

A complete physical examination will be performed by qualified staff (MD, DO, NP). New abnormal physical exam findings must be documented and will be followed by a physician or other qualified staff at the next scheduled visit.

Table 1. Procedures by Day**OVERVIEW**

| Days -30 to Day 0 (approx.) | Day 0 Baseline buprenorphine PK | | |
|---|---|--|--|
| Screening and assessment at CARI/Motivate facility including phenotyping battery (PhAB) | Outpatient visit to CRU for baseline buprenorphine PK measurement | | |
| | PK/Safety Testing Week 1, Day 1 | PK/Safety Testing Week 1, Day 2 - Day 3 | PK /Safety Testing Week 1, Day 4-7 |
| | Admit to CRU for overnight stay, urine drug screen, vital signs, physical examination, COWS | Lemborexant 5mg or placebo plus Buprenorphine-naloxone safety including pulse oximetry, agitation and sedation, PK, pupillometry, withdrawal, impulsivity measures, and subjective effects. | Follow-up at CARI/MOTIVATE for withdrawal, impulsivity measures, subjective effects, and side effects. |
| | PK/Safety Testing Week 2, Day 1 | PK/Safety Testing Week 2, Day 2 - Day 3 | PK/Safety Testing Week 2, Day 4-7 |
| | Admit to CRU, urine drug screen, vital signs, physical examination, COWS. Also stay overnight for safety and observation. | Lemborexant 10mg or placebo plus Buprenorphine-naloxone safety including pulse oximetry, agitation and sedation, PK, pupillometry, withdrawal, impulsivity measures, and subjective effects. | Follow-up at CARI/MOTIVATE for withdrawal, impulsivity measures, subjective effects, and side effects. |

Schedule of Procedures and Assessments:

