Pregnancy Test

A urine pregnancy test will be obtained from female subjects who are of childbearing age prior to their participation in the study.

Urinalysis

Urine will be obtained and sent to the clinical laboratory for determination of color, specific gravity, pH, protein, glucose, ketones, and blood.

Urine Drug Screen

Urine will be obtained from all subjects to be tested for cocaine (benzoylecgonine), opiates and opioids, benzodiazepines, fentanyl, amphetamine, methamphetamine, and THC.

Breathalyzer or salivary alcohol level

Breath or salivary alcohol level will be obtained from all subjects. Subjects who have a positive breath or salivary alcohol will be told that they must return at a later date with a negative alcohol test in order to take part in study procedures.

Pharmacokinetic Measurements

Pharmacokinetic samples for analysis of buprenorphine and its metabolites: Blood samples for analysis of the pharmacokinetics of buprenorphine-naloxone dose and lemborexant 5 and 10mg will be collected at baseline on day 0, and on PK/Safety Testing week 1, day 2, PK/Safety Testing week 2, day 2. After separation of plasma by routine methods, samples will be frozen at -70°C until ready for analysis. Plasma concentrations of buprenorphine and metabolite (norbuprenorphine) and lemborexant and metabolite (M10) will be assayed by liquid chromatography-tandem mass spectrometry.

Pupilometry measurement

Pupilometry is used to measure change in pupil size as an indicator of central nervous system mu-opioid pharmacological effects (Rollins, Feiner et al. 2014). Change in pupil size, as measured by single pupil

| Table 3. Schedule for blood samples for PK testing | | |
|--|---|---|
| Day 0 Baseline Buprenorphine PK | PK/Safety Week 1, Day 2 (and similarly Week 2, Day 2) | PK/Safety Week 1, Day 3 (and similarly Week 2, Day 3) |
| | 7:00 am (Pre-lemborexant dose at 7:05) | 7:00 am (if still on inpatient unit) |
| | 7:30 | |
| 8:00 am (Pre-buprenorphine dose at 8:05) | 8:00 am (Pre-buprenorphine dose at 8:05) | 8:00 am (pre-buprenorphine dose at 8:05) |
| 8:15 | 8:15 | |
| 8:30 | 8:30 | |
| 8:45 | 8:45 | |
| 9:15 | 9:15 | |
| 9:30 | 9:30 | |
| 10:00 | 10:00 | |
| 10:30 | 10:30 | |
| 11:00 | 11:00 | |
| 11:30 | 11:30 | |
| 12:00 | 12:00 | |
| 2:00 | 2:00 | |
| 4:00 | 4:00 | |

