mg doses), using a generalized linear mixed model analysis with the participant as a random effect for each outcome. Adverse event data will be compiled for lemborexant and placebo cohorts and presented as summary statistics.

2. Buprenorphine PK: Plasma concentration-time profiles of buprenorphine and its metabolite norbuprenorphine after doses during the lemborexant placebo/administration (Day 0, 1, 2) will be analyzed to obtain pharmacokinetic parameter estimates of buprenorphine (Cmax, Tmax, AUC, apparent t_{1/2}, CL/F for parent buprenorphine and metabolic (AUC) ratios for metabolites) by individual. These parameters will be compared within subjects on sessions with lemborexant. Lemborexant PK will be compared with published lemborexant PK data. As it would be unethical to withhold buprenorphine treatment from patients who are on buprenorphine for MAT, there will be no lemborexant dose without buprenorphine.

3. Changes in secondary outcome measures induced by lemborexant dose along with buprenorphine will be compared to those without lemborexant, by lemborexant dose level (5 mg and 10 mg doses), using a generalized linear mixed model analysis with the participant as a random effect for each outcome.

Safety and tolerability data will be summarized by treatment group.

Adverse event rates will be coded by body system and MedDra classification term. Adverse events will be tabulated by treatment group and will include the number of patients for whom the event occurred, the rate of occurrence, and the severity and relationship to study drug.

Interim Analysis

There will be no formal interim analysis.

Rationale for sample size: Sample size for effect of lemborexant on recommendations from the FDA regarding phase I safety studies.

DATA COLLECTION, RETENTION AND MONITORING

Data Collection Instruments

The Investigator will prepare and maintain adequate and accurate source documents designed to record all observations and other pertinent data for each subject treated with the study drug.

Study personnel at each site will enter data from source documents corresponding to a subject's visit into the protocol-specific paper/electronic CRF when the information corresponding to that visit is available. Subjects will not be identified by name in the study database or on any study documents to be collected by the Sponsor (or designee), but will be identified by a subject number.

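### Hypothesis 1 sets buprenorphine PK against placebo, but the only PK comparison rule is within subjects on lemborexant sessions and gives the randomised placebo arm no role

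*Combined protocol and SAP*

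**What the plan says.** Study Hypotheses, item 1: "Adjunctive lemborexant (compared to placebo) will not alter the PK of buprenorphine-naloxone significantly".

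The Synopsis (Primary Analysis Plan) and Statistical Methods and Considerations (primary outcome 2) both say that PK parameters are estimated for each individual, with placebo sessions included. Both then give one comparison rule: "These parameters will be compared within subjects on sessions with lemborexant". Neither names a reference session or a between-group contrast. Study Outcome Measures restates the outcome without any comparison for buprenorphine.

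The mixed models in the statistical sections are written for safety and secondary outcomes (in the Synopsis also exploratory ones), not for PK. The one explicit between-arm sentence, "All measures will be compared between subjects receiving lemborexant versus those on placebo", stands under Secondary Outcome Measures.

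Sampling: blood "will be collected at baseline on day 0, and on PK/Safety Testing week 1, day 2, PK/Safety Testing week 2, day 2". Table 1 describes Day 0 as "Outpatient visit to CRU for baseline buprenorphine PK measurement". Before each treatment session, by contrast, "Participants will spend the night on the CRU prior to lemborexant administration to ensure that they do not take any additional drugs or medications". AUC is defined under Study Drug and Dosage as running "from Time 0 post-dose to infinity".

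**The concern.** The hypothesis and the rule answer different questions. The hypothesis asks whether exposure changes more on lemborexant than on placebo. The rule asks whether exposure changes across sessions in people who take lemborexant. The answers agree only if nothing else changes between Day 0 and the later sessions.

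Several things do change. Day 0 is always first, 5 mg always precedes 10 mg, and only the treatment sessions follow a supervised night on the unit. If any of these shifts buprenorphine exposure, the shift is read as an interaction or hides one. The placebo group is the only part of the trial that could show which. Its planned profiles (6 × 3 = 18 of 18 × 3 = 54) are to be collected, and parameters estimated from them, with no stated use in the comparison. Leaving this open also means that the comparator for a primary outcome could be settled after results are seen.

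A second, smaller matter is AUC. Sampling stops much earlier on Day 0 than it can in the treatment sessions, so AUC to infinity is extrapolated from different windows.

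**Working it through.** The plan gives no PK calculation to reproduce. Its only figure is 12 + 6 = 18, with no CV, margin or confidence level. The CVs, session ratios, half-lives and the 90% level below are therefore assumptions.

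**1. What a session effect does.** Let D be the true drug ratio and S the session ratio to Day 0. The lemborexant arm estimates D × S and the placebo arm estimates S. With D = 1 and S = 1.10, the within-lemborexant ratio is 1.10 on average. Dividing by the placebo ratio gives 1.10 / 1.10 = 1.00, provided both arms share S.

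**2. What the correction costs.** The SD of a log change from Day 0 is √(2 ln(1 + CV²)), which is 0.280, 0.415 and 0.545 at CV 20%, 30% and 40%. The SE multiplies this by √(1/12) = 0.289 for lemborexant alone, or by √(1/12 + 1/6) = 0.500 for the quotient. The ratio is 0.500 / 0.289 = 1.73 at any CV. In a three-session mixed model the residual df are 18 × 2 − 2 − 2 = 32, with t(0.95, 32) = 1.694. The 90% interval around a true ratio of 1 is exp(±1.694 × SE):

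| CV | Lemborexant vs Day 0 | Divided by placebo ratio |
|---|---|---|
| 20% | 0.872–1.147 | 0.789–1.268 |
| 30% | 0.816–1.225 | 0.704–1.421 |
| 40% | 0.766–1.305 | 0.630–1.586 |

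For CV 30%: 0.415 × 0.289 = 0.120 and exp(1.694 × 0.120) ≈ 1.225; 0.415 × 0.500 = 0.208 and exp(1.694 × 0.208) ≈ 1.421 (results from unrounded values).

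**3. When the correction pays.** The uncorrected mean squared error is SD²/12 + (ln S)²; the corrected one is SD²/12 + SD²/6. They are equal at S = exp(SD × √(1/6)), which is 1.12, 1.18 and 1.25 (or 0.89, 0.84 and 0.80) at the three CVs. Nearer to 1, the uncorrected ratio is the better estimate.

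**4. Completeness.** Steps 2 and 3 assume that all 18 complete all three sessions. The Synopsis counts a participant with at least one treatment session. If 12 lemborexant but only 4 or 3 placebo participants had a given session, the simple two-sample SE ratio would be √(1/12 + 1/4) / √(1/12) = 2.00 or √(1/12 + 1/3) / √(1/12) = 2.24.

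**5. Sampling window.** In the blood-sampling table, buprenorphine is given at 8:05. The last Day 0 sample is at 4:00 pm, after 7 h 55 min. The Day 3 sample at 8:00 am comes after 23 h 55 min. So 7.92 / 23.92 = 33% of the longer window is observed on Day 0. Thirteen clock times from 8:00 am to 4:00 pm are common to all three sessions. A window that short responds weakly to clearance. Under monoexponential decline with half-life h and k = ln 2 / h, a clearance fall that raises AUC to infinity by 1.25 raises AUC to 7.92 h by 1.25 × (1 − exp(−7.92k/1.25)) / (1 − exp(−7.92k)). This is 1.12, 1.04 and 1.02 at half-lives of 4, 12 and 24 h.

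**The case against.** The best reply is that the within-subject contrast is sensible and probably what was meant. Day 0 is labelled baseline in the tables, is listed just before the rule, and is the only lemborexant-free PK session in that arm. That stands. A reader might infer that the comparison has no reference, or means only 5 mg against 10 mg. The literal sentence permits this, but the rest of the protocol points to Day 0.

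Second, a session effect is only a possibility, and the protocol limits it. All three sessions use the same unit, a buprenorphine dose equivalent to the prescription, and the same clock times. Table 2 schedules a drug screen and alcohol test on Day 0 too, and concomitant medication is to be kept constant in stabilised patients. That also stands. A reader might make much of the smoking ban, but "Subjects will not be allowed to smoke cigarettes, as smoking is not allowed in the hospital or anywhere on the VCU campus", so it covers the Day 0 visit as well. Only the preceding night differs.

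Third, step 3 shows that for a small session effect the uncorrected ratio is the better estimate. That stands too, and is why both are needed. It does not justify leaving the placebo profiles out, because without them nobody can judge whether the session effect is small.

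Fourth, a reader might infer that discharge on Day 2 will leave many without the 23 h 55 min sample. The documents give that little support: the inpatient condition in the sampling table is attached to the 7:00 am sample on Day 3, not the 8:00 am one, and Day 3 has an outpatient location in Table 2.

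**Conclusion.** The mismatch in the text is certain: hypothesis 1 is against placebo, the PK rule is not, and no other section closes the gap. Followed literally, the rule confounds lemborexant with session.

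The stronger reading, that the planned comparison is biased or would give a wrong answer, is not supported. No session effect is documented, its direction is unknown, and several features limit it. What can be said is conditional: any session ratio enters the result one for one, and the placebo arm can remove it at an SE 1.73 times larger. That figure holds for 12 against 6 with all sessions complete, so it is a best case. The intervals also rest on assumed CVs. Nor is the placebo arm absent from PK altogether: its parameters are to be estimated, and what is missing is their role in the comparison.

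The difference in AUC windows is real but secondary. Seriousness lies between minor and should-fix; confidence is high for the mismatch only.

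**What to change.** Replace the comparison sentence in the Synopsis and in Statistical Methods with wording such as:

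*Day 0 is the lemborexant-free reference. For log-transformed Cmax and AUC, each treatment session is compared with Day 0 within participant in both groups. The within-lemborexant ratio, the placebo-group ratio and their quotient, from a mixed model with group, session, group × session and a participant random effect, are reported with confidence intervals.*

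Declare the confidence level, since the documents set none, and report how many participants contribute to each session. The least that would serve is to show the Day 0 comparison for the placebo group alongside that for lemborexant.

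For AUC, add AUC from dose to 4:00 pm as a supporting like-for-like comparison beside AUC to infinity, not in place of it. State the sampled window for each session, and state that the short window is insensitive to a change in clearance.

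Cost: no new visits, samples or participants. It is an amendment needing prior written IRB approval, and the added AUC must be declared as an addition to the existing definition. The placebo-corrected ratio will be imprecise with six controls and, alone, gives weaker support for no alteration; hence both ratios are reported.
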